8.3.2. Method of Detecting Adverse Events, Adverse Events of Special Interest, and Serious Adverse Events

Care will be taken not to introduce bias when detecting AEs, suspected AESIs, or SAEs. Openended and nonleading verbal questioning of the participant is the preferred method to inquire about AE occurrence.

Solicited Adverse Events

Solicited AEs are used to assess the reactogenicity of the study vaccine and are predefined local (at the injection site) and systemic events for which the participant is specifically questioned and which are noted by participants in their diary.

After each vaccination, participants will remain under observation at the study site for at least 1 hour for the presence of any acute reactions and solicited events.

In addition, participants (or parents/legal guardians of the minor participants) will record solicited signs and symptoms in a diary for 7 days post-vaccination. All participants will be provided with a diary and instructions on how to complete the diary (see Overview in Section 8, Study Assessments and Procedures). Diary information will be transferred to the sponsor. After review and verbal discussion of the initial diary entries with the participant, the investigator will complete his/her own assessment in the relevant sections of the eCRF. Once a solicited sign or symptom from a diary is considered to be of severity Grade 1 or above, it will be recorded as a solicited AE.

Solicited Injection Site (Local) Adverse Events

Participants will be asked to note in the diary occurrences of injection site pain/tenderness, erythema and swelling at the study vaccine injection site daily for days post-vaccination (day of vaccination and the subsequent 7 days). The extent (largest diameter) of any erythema and swelling should be measured (using the ruler supplied) and recorded daily. The case definitions for solicited injection site events can be found in the references.^{0,0}

Solicited Systemic Adverse Events

Participants will be instructed on how to record daily temperature using a thermometer provided for home use. Participants should record the temperature in the diary in the evening of the day of vaccination, and then daily for the next 7 days approximately at the same time each day. If more than one measurement is made on any given day, the highest temperature of that day will be used in the eCRF.

Fever is defined as endogenous elevation of body temperature ≥38° C, as recorded in at least one measurement.⁰

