After each vaccination, participants will remain under observation at the study site for at least 1 hour to monitor for the presence of any acute reactions and solicited events.

Participants will also be instructed on how to note signs and symptoms in the diary on a daily basis for 7 days post-vaccination (day of vaccination and the subsequent 7 days), for the following events: fatigue, headache, nausea, and myalgia.

Unsolicited Adverse Events

Unsolicited AEs are all AEs for which the participant is not specifically questioned in the participant diary.

For details about AESIs, refer to Section 8.3.6.

8.3.3. Follow-up of Adverse Events, Adverse Events of Special Interest, and Serious Adverse Events

The investigator is obligated to perform or arrange for the conduct of supplemental measurements and evaluations as medically indicated to elucidate the nature and causality of the AE, suspected AESI, SAE, or PQC as fully as possible. This may include additional laboratory tests or investigations, histopathological examinations, or consultation with other health care professionals.

AEs, including pregnancy, will be followed by the investigator as specified in Section 10.4.

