10.4.3. Severity Criteria

All AEs and laboratory data will be coded for severity using a modified version of the FDA grading table, based on the version of September 2007⁰, included in Section 10.6.

For AEs not identified in the grading table, the following guidelines will be applied:

Grade 1	Mild	Symptoms causing no or minimal interference with usual social and functional activities
Grade 2	Moderate	Symptoms causing greater than minimal interference with usual social and functional activities
Grade 3	Severe	Symptoms causing inability to perform usual social and functional activities and requires medical intervention
Grade 4	Potentially life-threatening	Symptoms causing inability to perform basic self-care functions OR medical or operative intervention indicated to prevent permanent impairment, persistent disability OR ER visit or hospitalization

The severity of solicited signs and symptoms will be graded in the diary by the participant based on the severity assessment provided in the diary and then verified by the investigator using the toxicity grading scale in Section 10.6. (Note: severity of the measured events will be derived from the diameter [for erythema and swelling] and the temperature measurements [for fever])

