10.6. Appendix 6: Toxicity Grading Scale

Adapted from the FDA Guidance document "Toxicity Grading Scale for Healthy Adult and Adolescent Volunteers Enrolled in Preventive Vaccine Clinical Trials" (September 2007).

A: Tables for Clinical Abnormalities

Local Reaction to Injectable Product	Mild (Grade 1)	Moderate (Grade 2)	Severe (Grade 3)	Potentially Life Threatening (Grade 4)
Pain/Tenderness#	Aware of symptoms but easily tolerated; Does not interfere with activity; Discomfort only to touch	Notable symptoms; Requires modification in activity or use of medications; Discomfort with movement	Incapacitating symptoms; Inability to do work, school, or usual activities; Use of narcotic pain reliever	Hospitalization; Pain/tenderness causing inability to perform basic self- care function
Erythema#	25 – 50 mm	51 – 100 mm	> 100 mm	Hospitalization; Necrosis or exfoliative dermatitis
Swelling [#]	25 – 50 mm	51 – 100 mm	> 100 mm	Hospitalization; Necrosis

Revised by the sponsor.

Vital Signs *	Mild (Grade 1)	Moderate (Grade 2)	Severe (Grade 3)	Potentially Life Threatening (Grade 4)
Fever (°C) ** (°F)**	38.0 - 38.4 100.4 - 101.1	38.5 - 38.9 101.2 - 102.0	39.0 - 40.0 102.1 - 104.0	> 40 > 104.0
Tachycardia - beats per minute	101 – 115	116 – 130	> 130	Hospitalization for arrhythmia#
Bradycardia - beats per minute***	50 – 54	45 – 49	< 45	Hospitalization for arrhythmia#
Hypertension (systolic) - mm Hg	141 – 150	151 – 155	> 155	Hospitalization for malignant hypertension#
Hypertension (diastolic) - mm Hg	91 – 95	96 – 100	> 100	Hospitalization for malignant hypertension#
Hypotension (systolic) – mm Hg	85 – 89	80 – 84	< 80	Hospitalization for hypotensive shock [#]
Respiratory Rate – breaths per minute	17 – 20	21 – 25	> 25	Intubation

^{*} Participant should be at rest for all vital sign measurements.

^{**} For oral temperature: no recent hot or cold beverages or smoking.

^{***} When resting heart rate is between 60 - 100 beats per minute. Use clinical judgment when characterizing bradycardia among some healthy participant populations, for example, conditioned athletes.

[#] Revised by the sponsor.

Systemic (General)	Mild (Grade 1)	Moderate (Grade 2)	Severe (Grade 3)	Potentially Life Threatening (Grade 4)
Vomiting [#]	No interference with activity or 1 – 2 episodes/24 hours	Some interference with activity or > 2 episodes/24 hours	Prevents daily activity, requires outpatient IV hydration	Hospitalization; Hypotensive shock

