5.6.1. Adverse Events

5.6.1.1. Definitions

Solicited AEs shown in the tables are extracted from the investigator assessment pages (CE) of the CRF. For unsolicited AEs, only the AEs within the 28-day period following each vaccination will be presented in the safety tables except for SAEs, which will be captured and tabulated in the outputs covering the whole study period. All other collected unsolicited adverse events will be presented through listings.

Solicited administration site symptoms will be considered as related to the study vaccine (by definition).

The severity of the AEs will be classified as grade 1 to 4. Solicited events that are graded less than grade 1, are not considered as AE. In case no grades are available, the grading of the solicited events will occur according to the grading list in Appendix 3.

For AESI, the following is defined:

- Suspected AESI : as reported by investigator and presented by: Embolic and thrombotic events (SMQ) + PT; Haematopoietic thrombocytopenias (SMQ) (broad) or HLT Thrombocytopenias + PT; Other SMQ + PT.
- Suspected AESI: Embolic and thrombotic events (SMQ), Haematopoietic thrombocytopenias (SMQ) (broad) or HLT Thrombocytopenias and presented by: Embolic and thrombotic events (SMQ) + sub-SMQ1 + PT; Haematopoietic thrombocytopenias (SMQ) (broad) or HLT Thrombocytopenias + PT;
- Qualified for assessment AESI: [Embolic and thrombotic events (SMQ)] and [Haematopoietic thrombocytopenias (SMQ) (broad) or HLT Thrombocytopenias or platelet count below normal ranges per local or central laboratory report or platelet count < 150 × 10⁹/L] and presented by: Embolic and thrombotic events (SMQ) + sub-SMQ1 + PT;

^a As indicated previously, all analyses, including the safety analyses, will be conducted by actually received vaccine (“as treated” principle). The sentence “by study intervention regimens as designed per protocol” indicates that the statistical tables are designed with the planned vaccine regimens as columns. Therefore, participants who receive e.g. “Placebo, Placebo” instead of “Ad26.COV2.S 5x10¹⁰ vp, Placebo” will appear in the “Placebo, Placebo” column. However, to avoid sparse columns, participants who receive e.g. “Placebo, Ad26.COV2.S 5x10¹⁰ vp” (which is not a planned vaccine regimen) will be excluded from the statistical tables. They will be included in the listings, as well as in the programmed patient narratives where they will appear as “Subjects with vaccine misallocation”.

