5.6.1.4. Missing Data

Missing AE data will not be imputed. Participants who do not report an event will be considered as participants without an event. An AE with a missing severity or relationship will be considered as an AE reported, but will be considered as not reported for the severity or relationship. For example, an AE with missing severity will be considered as an AE reported for the analysis of any grade, but will be considered as not reported for the analysis of at least grade 3.

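### The SAP's fallback for solicited events without a recorded grade points to an appendix that can grade only fever; an erythema or swelling record with a diameter but no grade stays ungraded and is left out of the grade 3 or higher table

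*SAP*

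**What the plan says.** Protocol 8.3.2 solicits eight events. Three are local: participants "note in the diary occurrences of injection site pain/tenderness, erythema and swelling at the study vaccine injection site". Four are systemic symptoms, recorded daily "for the following events: fatigue, headache, nausea, and myalgia". The eighth is fever, taken from the daily temperature.

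Protocol 10.4.3 sets the main grading route. The participant grades each sign or symptom in the diary, and the investigator verifies it against the scale in protocol 10.6. For the measured events it adds that "severity of the measured events will be derived from the diameter [for erythema and swelling] and the temperature measurements [for fever". Protocol 10.6 has a table headed "Local Reaction to Injectable Product" and a table of systemic events. With its fever row, these cover all eight.

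SAP 5.6.1.1 names the data source: "Solicited AEs shown in the tables are extracted from the investigator assessment pages (CE) of the CRF". It then gives the fallback: "In case no grades are available, the grading of the solicited events will occur according to the grading list in Appendix 3". SAP 5.6.1.2 requires solicited-event tables by worst severity grade and at grade 3 or higher. SAP 5.6.1.4 says that missing AE data are not imputed, and that an event with missing severity counts in the any-grade analysis but "will be considered as not reported for the analysis of at least grade 3".

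**The concern.** The fallback exists so that a solicited event without a grade is not lost from the severity tables. It works only if the list it names can grade the event, and for seven of the eight solicited events SAP Appendix 3 has no entry.

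Solicited local and systemic events are a primary safety endpoint in adults and in adolescents (SAP 5.3). The missing-severity rule can remove events from the grade 3 or higher table but can never add any. Any error from a failed fallback therefore goes one way, towards fewer severe reactions. It matters most where the grade could have been worked out from a measurement on file.

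**Working it through.** There is no sample-size or power figure to reproduce. The check matches each solicited event against the two grading lists, then follows the SAP rules for a record without a grade.

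**1. Coverage of the grading lists**

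| Solicited event (protocol 8.3.2) | In SAP Appendix 3? | In protocol 10.6? | Basis of the grade in protocol 10.6 |
|---|---|---|---|
| Pain/tenderness | No | Yes | Symptoms, effect on activity, medication |
| Erythema | No | Yes | Diameter (Grades 1 to 3) |
| Swelling | No | Yes | Diameter (Grades 1 to 3) |
| Fatigue | No | Yes | Symptoms, effect on activity |
| Headache | No | Yes | Symptoms, effect on activity |
| Nausea | No | Yes | Symptoms, effect on activity |
| Myalgia | No | Yes | Symptoms, effect on activity |
| Fever | Yes (vital signs) | Yes | Temperature |

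Solicited events: 3 + 4 + 1 = 8. Covered by SAP Appendix 3: 1. Not covered: 8 − 1 = 7. Covered by protocol 10.6: 8.

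**2. Which gaps could be closed at analysis**

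A programmer can assign a missing grade only from something recorded. Fever has a temperature and is already covered. Erythema and swelling have a diameter. The other five are graded on a judgement of interference, medication or bed rest. If neither participant nor investigator recorded a grade, a copied table generally gives nothing to derive one from. The gap that can be corrected is therefore mainly two events.

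**3. Tracing one record**

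Take an erythema record with a diameter above 100 mm and no grade.

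- Protocol 10.6: 25 to 50 mm is Grade 1, 51 to 100 mm is Grade 2, and above 100 mm is Grade 3. The record is Grade 3.
- SAP 5.6.1.1 sends it to SAP Appendix 3, which has no erythema row. Severity stays missing.
- SAP 5.6.1.4 counts it as any grade and does not count it as grade 3 or higher.

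**4. Size per affected participant**

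The tables count participants with at least one event, so one lost record changes a row by at most one participant.

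- Planned adult group of 75 (Groups 1 to 5): 1/75 = 1.3 percentage points.
- Adolescents given active vaccine at Day 1 (protocol 4.1): sentinels 5 + 5 = 10, safety cohort 10 + 10 = 20, total 30. 1/30 = 3.3 points.

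These are upper limits for a table with that denominator. The change is zero if the participant has another grade 3 or higher event in the same row and period. For Group 1 the step is smaller, because SAP Appendix 2 adds most of Group 7 to it for safety. In tables with fewer participants, such as those by age group, it is larger in proportion.

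**The case against.** The strongest reply is that the fallback will rarely be needed. The participant grades in the diary, the investigator verifies with a complete scale, and the SAP builds its tables from the investigator's pages. Protocol 10.4.3 already requires erythema and swelling to be graded from the diameter, and nothing in the SAP revokes that. An analyst who knows the protocol would use its cut-offs.

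Much of this stands, and it rules out two stronger readings. A reader might infer that all events of the seven uncovered types drop out of the grade 3 or higher tables. The documents do not support that: the rule applies only where no grade is available, and an event graded on the investigator pages is tabulated normally. A reader might also infer that local reactions below 25 mm would be counted as adverse events, because an ungraded record cannot be tested against Grade 1. That does not follow either. Protocol 8.3.2 has a sign or symptom recorded as a solicited AE only once it is judged Grade 1 or above, so this filter acts at recording.

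What does not stand is leaving the pointer to the analyst's knowledge. SAP Appendix 3 is not an abridged copy of the protocol scale. Its Grade 4 entry for tachycardia includes an emergency-room visit, whereas the sponsor-revised protocol entry is hospitalization only. The protocol also marks its pain, erythema and swelling entries as sponsor-revised, so the guidance named in the title of Appendix 3 cannot be assumed to give the same grades. The SAP defers several other details to the Data Presentation Specifications, but not this one.

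**Conclusion.** The cross-reference fails: SAP Appendix 3 can grade one of the eight solicited events. The consequence is narrow. It concerns records without a grade, and among those mainly erythema and swelling with a diameter on file. For these, the SAP as written returns a missing severity where the protocol gives a grade, and the error can only lower the grade 3 or higher rate of a primary safety endpoint.

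The total effect cannot be computed. The documents do not say how many solicited events lack a grade, and the number may be zero. They also do not show whether the investigator pages hold a grade for erythema and swelling or only a diameter; exposure would be greatest in the second case. The 1.3 and 3.3 points are upper limits per affected participant. They assume full denominators of 75 and 30, with adolescent Groups A and B taken together, and no other grade 3 or higher event in the same row. They are not estimates of bias in the trial. The documents support a faulty rule, not a finding that severe reactogenicity has been understated.

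**What to change.** In SAP 5.6.1.1, replace the pointer to Appendix 3 with one to the local and systemic tables of protocol Section 10.6, keeping the fever row, or copy those two tables into SAP Appendix 3. Add one sentence: where erythema or swelling has a recorded diameter and no grade, the grade is derived from the diameter with the protocol 10.6 cut-offs. Say that this derivation comes before the missing-severity rule of SAP 5.6.1.4 and is not imputation. The diameter settles Grades 1 to 3 only; Grade 4 in that table rests on hospitalization or tissue findings and must still come from the investigator.

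For pain, fatigue, headache, nausea and myalgia, the pointer supplies the correct definitions but will seldom recover a missing grade. A footnote giving the number of solicited events with missing severity, by group, would show whether the issue matters at all.

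The cost is one changed cross-reference, one or two added sentences and, if preferred, two copied tables. No new data are needed and no clinical definition changes.

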All SAEs and AEs leading to discontinuation from the study/vaccination (regardless of the causal relationship) are to be reported for all participants from the moment of first vaccination until completion of the participant's last study-related procedure, which may include contact for safety follow-up. The sponsor will evaluate any safety information that is spontaneously reported by an investigator beyond the time frame specified in the protocol.

All AEs will be followed until resolution or until clinically stable.

Adverse Events of Special Interest

From the time of local approval of protocol Amendment 5 onwards, TTS is considered to be an AESI. Suspected AESIs (thrombotic events and thrombocytopenia [defined as platelet count below $150,000/\mu L^0$]) will be recorded from the moment of vaccination until the end of the study/early withdrawal. An AESI Adjudication Committee with appropriate expertise will be established to evaluate each suspected AESI and determine whether it is a case of TTS. (see Section 8.3.6).

Serious Adverse Events

All SAEs, as well as PQC, occurring during the study must be reported to the appropriate sponsor contact person by study-site personnel within 24 hours of their knowledge of the event.

SAEs, including those spontaneously reported to the investigator, must be reported using an SAE form. The sponsor will evaluate any safety information that is spontaneously reported by an investigator beyond the time frame specified in the protocol.

Information regarding SAEs will be transmitted to the sponsor using the Serious Adverse Event Form and Safety Report Form of the CRF, which must be completed and reviewed by a physician from the study site and transmitted to the sponsor within 24 hours. The initial and follow-up reports of an SAE should be transmitted electronically or by facsimile (fax). Telephone reporting should be the exception and the reporter should be asked to complete the appropriate form(s) first.

Adolescents

Signs and symptoms of Multisystem Inflammatory Syndrome in Children (MIS-C) will be monitored and reported as SAE in children with (suspected) COVID-19 as confirmed by a positive RT-PCR result for SARS-CoV-2, and in children of mothers or close relatives with prior (within 4-weeks) or current suspected or confirmed COVID-19. Further details on case definition and reporting of MIS-C in children can be found in section 10.12.

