8.3.6.1. Thrombosis with Thrombocytopenia Syndrome (TTS)

As described in Section 2.3.1, Risks Related to Study Participation, TTS has been observed very rarely following vaccination with Ad26.COV2.S and is considered to be an AESI in this study. TTS is a syndrome characterized by a combination of both a thrombotic event and thrombocytopenia.

Because this syndrome is rare and not completely understood, all cases of thrombosis and/or thrombocytopenia will be considered a suspected case of TTS until further adjudication can be performed. An AESI Adjudication Committee with appropriate expertise will be established to evaluate each suspected AESI and determine whether it is a case of TTS. The investigator shall be responsible for reporting any suspected AESI of TTS using the SAE form and the form detailed in Section 10.13, Appendix 13. A suspected TTS case is defined as:

- Thrombotic events: suspected deep vessel venous or arterial thrombotic events as detailed in Section 10.14, Appendix 14 OR,
- Thrombocytopenia, defined as platelet count below 150,000/μL⁰

Symptoms, signs, or conditions suggestive of a thrombotic event should be recorded and reported as a suspected AESI even if the final or definitive diagnosis has not yet been determined, and alternative diagnoses have not yet been eliminated or shown to be less likely. Follow-up information and final diagnoses, if applicable, should be submitted to the sponsor as soon as they become available.

In the event of thrombocytopenia, study site personnel should report the absolute value for the platelet count and the reference range for the laboratory test used.

For either a thrombotic event or thrombocytopenia, testing for anti-PF4 should be performed at the local laboratory or substitute local laboratory; repeat testing may be requested for confirmation upon sponsor discretion.

Suspected AESIs will require enhanced data collection and evaluation (see Section 1.3.8). Every effort should be made to report as much information as possible about the AESI to the sponsor in a reasonable timeframe.

If an event meets the criteria for an SAE (Section 10.4.1), it should be reported using the same process as for other SAEs.

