1. INTRODUCTION

This SAP describes the pre-planned analyses for the Interim Analyses, Primary Analyses and Final Analysis, for all groups in the study. One or several Data Presentation Specification Documents will be available to further detail the statistical outputs that will be generated.

For some analyses (e.g. RNA sequencing data), a separate SAP may be written.

Due to the reactogenicity observed at the 2.5×10^{10} vp dose level, it was decided not to proceed to the 5×10^{10} vp dose level in adolescents.

Safety, reactogenicity and immunogenicity data will be summarized for the 33 enrolled adolescent participants. Only limited outputs will be provided.

The term “study vaccine” throughout the SAP, refers to Ad26.COV2.S or placebo as defined in Clinical Trial Protocol Section 6.1, Study Vaccinations Administered. Scientifically, the administration of the Ad26.COV2.S 1.25×10^{10} virus particles (vp) or placebo dose 4 months after the primary vaccination regimen in adults is considered as presentation of antigen. Nevertheless, for the sake of simplicity, the terms “study vaccine” and “vaccination” throughout the SAP encompass administration of the antigen presentation dose.

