5.3. Primary Endpoint(s) Analysis

The primary endpoints in this study, are:

Adults

Humoral Immune Response

All participants in groups 1-3 (3 dose levels of Ad26.COVS.S administered as a 2-dose schedule at a 56-day interval):

- Serological response to vaccination as measured by virus neutralization assay (VNA) titers and enzyme-linked immunosorbent assay (S-ELISA EU/mL), 28 days after Vaccination 2.
- Antibody geometric mean titers (GMTs) (VNA) and geometric mean concentrations (GMCs) (S-ELISA), 28 days after Vaccination 2.

All participants in groups 4-5 (2 dose levels of Ad26.COVS.S administered as a single vaccination):

- Serological response to vaccination as measured by VNA titers and ELISA (S-ELISA EU/mL), 28 days after Vaccination 1.
- Antibody GMTs (VNA) and GMCs (S-ELISA), 28 days after Vaccination 1.

All participants in groups 7-9 (5×10^{10} vp dose level, administered as a 2-dose schedule at a 28-day and at an 84-day interval):

- Serological response to vaccination as measured by VNA titers and ELISA (S-ELISA EU/mL), 28 days after Vaccination 2.
- Antibody GMTs (VNA) and GMCs (S-ELISA), 28 days after Vaccination 2.

Safety and reactogenicity of Ad26.COVS.S

- Solicited local and systemic AEs for 7 days after each vaccination.
- Unsolicited AEs for 28 days after each vaccination.
- Serious adverse events (SAEs) and adverse events of special interest (AESIs) throughout the study (from first vaccination until end of the study)

Adolescents

Safety and reactogenicity of Ad26.COVS.S

- Solicited local and systemic AEs for 7 days after vaccination.
- Unsolicited AEs for 28 days after vaccination.
- SAEs (incl. Multisystem Inflammatory Syndrome in Children [MIS-C]) and AESIs throughout the study (from first vaccination until end of the study).

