Safety analyses will be performed on the FAS. Continuous variables will be summarized using the following statistics, as appropriate: number of observations, arithmetic mean (mean), standard deviation (SD), standard error (SE), median, quartiles (Q1 and Q3), minimum and maximum. Frequencies and percentages (one decimal place) will be generated for categorical variables. No formal comparisons between groups will be provided.

Safety data will be analyzed by study intervention regimens as designed per protocol^a. In addition, safety data will be analyzed by intervention regimens as designed per protocol and age group. Data will be presented by period (post Dose 1, post Dose 2, post Antigen Presentation, as applicable) as well as over the entire primary regimen, and over the entire Antigen Presentation regimen. Denominator for the percentages is the number of participants in the considered population and phase for a certain regimen (incidence per 100 participants/phase).

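### The SAP stops at suspected and screen-positive AESIs: no category or table uses the Adjudication Committee's TTS decision, and AESIs after the crossover injections may appear only in listings

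*SAP*

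**What the plan says.** SAP 5.3 lists among the adult primary endpoints "Serious adverse events (SAEs) and adverse events of special interest (AESIs) throughout the study (from first vaccination until end of the study"), with a matching entry for adolescents.

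Protocol 8.3.1 says what the AESI is: "From the time of local approval of protocol Amendment 5 onwards, TTS is considered to be an AESI". Protocol 8.3.6.1 treats any thrombosis and/or thrombocytopenia as suspected until reviewed, and says who decides: "An AESI Adjudication Committee with appropriate expertise will be established to evaluate each suspected AESI and determine whether it is a case of TTS".

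SAP 5.6.1.1 then defines three AESI categories:

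- "Suspected AESI : as reported by investigator and presented by: Embolic and thrombotic events (SMQ) + PT", and further groupings;
- "Suspected AESI: Embolic and thrombotic events (SMQ), Haematopoietic thrombocytopenias (SMQ) (broad) or HLT Thrombocytopenias and presented by" SMQ, sub-SMQ and preferred term;
- "Qualified for assessment AESI: [Embolic and thrombotic events (SMQ)] and [Haematopoietic thrombocytopenias (SMQ) (broad"), or alternatively the thrombocytopenia high-level term or a low platelet count.

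Three other SAP rules decide where an AESI is shown:

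- Section 5.6.1.1 limits unsolicited-AE tables to 28 days after each vaccination, excepts only SAEs, and sends the rest to listings.
- Section 5.1.2 builds the 'Entire Period' from Dose 1 to follow-up after antigen presentation. It mentions SAEs but not AESIs.
- Section 4 censors the safety analyses at unblinding or at an outside COVID-19 vaccine, whichever is first, and lists later AEs.

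**The concern.** The endpoint and its analysis do not meet. A suspected AESI is an input to the committee, and TTS is the output. If the SAP is followed literally, an event the committee confirms and one it rejects fall in the same category, and no line of the report says how many participants had TTS.

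The second issue is placement. For adults, prospective AESI reporting begins with local approval of Amendment 5, and general unblinding comes with implementation of the same amendment. Censoring at unblinding therefore removes from the tables much of the time in which AESIs were prospectively reported, including all of the crossover vaccination. For a primary endpoint that runs to the end of the study, that should be a stated choice, not a side effect of three separate rules.

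**Working it through.** **1. Is the committee's decision used anywhere in the SAP?** The three categories in 5.6.1.1 rest on the investigator's report, on coded terms, and on coded terms plus platelet values. The table list for unsolicited AEs in 5.6.1.2 covers a summary, all events, most frequent, grade 3 or higher, permanent stop of vaccine, related, and SAE. It has no AESI or TTS table. The listing and narrative sentence in 5.6.1.2 covers deaths, vaccination discontinuations and severe or serious AEs, but not AESIs, although protocol 9.4.2 names AESIs. Neither TTS nor adjudication is mentioned in the supplied SAP. This is the current AESI text: the SAP version history gives clarifications on AESI as part of version 3.

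**2. Where would particular events appear?**

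- TTS confirmed by the committee, 10 days after Dose 1: in the suspected and qualified categories, not labelled as TTS.
- The same presentation, rejected by the committee: in the same categories, indistinguishable from the first.
- Non-serious thrombocytopenia 40 days after antigen presentation: beyond 28 days and not an SAE, so listings only under 5.6.1.1.
- TTS confirmed by the committee, 10 days after a first crossover dose: after unblinding (Section 4) and outside the 'Entire Period' (5.1.2). The periods named for display in 5.1.2 and 5.6 do not include cross-vaccination.

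The last result is 'may', not 'will'. SAP Table 1 does define cross-vaccination phases, 5.6.1.1 promises SAE tables over the whole study, and protocol 9.4.2 says adult data are analysed separately from unblinding. Section 4 does not say how it fits with these.

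**3. How many injections are affected?** Planned group sizes are from protocol 4.1 (Table 2 and the adolescent text).

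- Active injections before Amendment 5: Groups 1-3, 225 × 3 = 675. Groups 4-5, 150 × 2 = 300. Groups 7 and 9, 100 × 3 = 300. Adolescents, 30. Total 1305.
- Active injections after: 75 placebo adults × 2 = 150, plus 3 in Group C = 153, in 78 participants.
- Share after: 153 / 1458 = 10.5%. Share before: 89.5%.

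This takes all adult Injections 1-3 as given before Amendment 5, as the Amendment 6 summary of changes and the visit order in protocol 1.3.1-1.3.3 indicate. Protocol 6.3 instead describes antigen presentation as given unblinded with Amendment 5. On that reading the injections before are 1305 − 475 = 830 (56.9%) and those after are 628. The passages need to be reconciled.

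**4. Precision.** The only stated safety precision is protocol Table 9. The zero-event one-sided 95% limit, 1 − 0.05^(1/n), gives 11.29%, 5.82%, 3.92% and 1.98% for n = 25, 50, 75 and 150, matching the table's 11.3%, 5.8%, 3.9% and 2.0%. For planned regimens of 50 or 75 participants the limit is thus 5.8% or 3.9%. For the 75 crossover adults it is also 3.9%.

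**The case against.** The best defence is that the SAP is not the last word on outputs: "One or several Data Presentation Specification Documents will be available to further detail the statistical outputs that will be generated". The committee's charter is also not supplied, and protocol 9.4.2 allows summaries, listings or narratives for participants with an AESI. The study is descriptive, TTS is described as very rare, and a narrative could report one case adequately. This lowers the severity, but nothing in the SAP requires those documents to carry the committee's decision.

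Three stronger readings are tempting, and the documents do not support them.

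- *A reader might infer that AESI rates will be shown on all 475 planned active adults as if all had been prospectively observed.* No such table is planned. SAP 5.1.5 analyses by group unless pooling is stated, and 5.6 says: "Denominator for the percentages is the number of participants in the considered population and phase for a certain regimen".
- *A reader might infer that TTS before Amendment 5 went uncollected.* SAEs and AEs leading to discontinuation were reportable from first vaccination, and other unsolicited AEs for 28 days after each dose. Protocol 2.3.1 puts onset at about 1-2 weeks, within that window. Protocol 8.3.6.1 adds an attempt to collect information on events reported earlier. What remains is non-serious events beyond 28 days and clinically silent thrombocytopenia, since the routine panel in protocol Appendix 2 has no platelet count.
- *A reader might infer that the third category is faulty because it sets no time link between thrombosis and low platelets.* Its label marks it as a screen for review, and the protocol keeps suspicion deliberately wide. An undefined same-episode condition could remove cases before the committee sees them.

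**Conclusion.** The point holds in this form. A primary safety endpoint whose case status belongs to a committee has no SAP category or table that uses the committee's decision. As written, the report gives suspected and screen-positive events and no count of TTS. In addition, the 28-day limit, the 'Entire Period' and censoring at unblinding together may leave AESIs after the crossover injections in listings only. By planned counts these are 153 active injections in 78 participants, 10.5% of all active injections.

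Assumptions: planned, not actual, numbers; full crossover uptake; Injection 3 completed before Amendment 5; Section 4's censoring applies to the general unblinding under Amendment 5; and no further requirement in documents not supplied. If uptake were 75% or 50%, the share after would be 8.1% or 5.5%.

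The documents do not show that TTS rates would be misstated by any particular factor, or that cases were missed. Severity: should-fix.

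**What to change.** In SAP 5.6.1.1 and 5.6.1.2:

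1. Add adjudicated TTS (committee decision) as the headline AESI category. Tabulate it by regimen and phase over the whole study, explicitly including the cross-vaccination phases and stating that neither the 28-day limit nor the censoring in Section 4 applies to it. Keep the three existing categories unchanged as supporting screens.
2. Flag each AESI by whether its onset was before or after local approval of Amendment 5. The flag belongs to the event date, because someone injected earlier and still in follow-up comes under AESI reporting from that approval.
3. Footnote the AESI tables: before that approval, non-serious events more than 28 days after a dose and clinically silent thrombocytopenia were not systematically collected.
4. Align 5.1.2 and Section 4 with this, and reconcile the protocol passages on when antigen presentation was given.

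Cost: SAP wording, one variable from an adjudication the protocol already requires, one onset flag and one table shell. No new data collection.
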